6.5.7 Magnetic resonance Imaging (MRI)

Magnetic resonance imaging with gadolinium (MRI) will be used to assess the structural integrity of the inner to determine if the patients study ear is suitable for enrolling the trial as well as following treatment to assess the inner ear structural integrity and evaluate for other potential complications of treatment, including labyrinthitis ossificans. The imaging acquisition will follow the local facility procedures indicating the specific hardware and software settings for acquisition of all inner ear structural parameters.

6.6 Pharmacokinetic assessments

Not applicable.

6.7 Other assessments

Not applicable.

Commercially Confidential Information

7 Safety monitoring

7.1 Adverse events

An adverse event (AE) is any untoward medical occurrence (i.e., any unfavorable and unintended sign [including abnormal laboratory findings], symptom or disease) in a patient or clinical investigation patient *after providing written informed consent* for participation in the study. Therefore, an AE may or may not be temporally or causally associated with the use of a medicinal (investigational) product. Pre-existing medical conditions/diseases (i.e., Medical History(ies)) are considered AEs if they worsen after providing written informed consent. Abnormal laboratory values or test results constitute AEs only if they induce clinical signs or symptoms, or are considered clinically significant, or they require therapy.

The occurrence of adverse events should be sought by non-directive questioning of the patient at each visit during the study. Adverse events also may be detected when they are volunteered by the patient during or between visits or through physical examination, laboratory test, or other assessments.

Adverse events must be recorded on the Adverse Events CRF under the signs, symptoms or diagnosis associated with them, and accompanied by the following information:

- 1. the severity grade:
 - mild: usually transient in nature and generally not interfering with normal activities
 - moderate: sufficiently discomforting to interfere with normal activities
 - severe: prevents normal activities
- 2. its relationship to study treatment
- 3. its duration (e.g., start and end date)
- 4. whether it constitutes a serious adverse event (SAE)
- 5. action taken regarding study treatment
- 6. whether other medication or therapies have been taken (concomitant medication / non-drug therapy)
- 7. its outcome

An SAE is defined as any AE which meets any one of the following criteria:

- is fatal or life-threatening
- results in persistent or significant disability/incapacity
- constitutes a congenital anomaly/birth defect
- requires inpatient hospitalization or prolongation of existing hospitalization, unless hospitalization is for:
 - routine treatment or monitoring of the studied indication, not associated with any deterioration in condition
 - elective or pre-planned treatment for a pre-existing condition that is unrelated to the indication under study and has not worsened since signing the informed consent form
 - treatment on an emergency outpatient basis for an event not fulfilling any of the definitions of a SAE given above and not resulting in hospital admission
 - social reasons and respite care in the absence of any deterioration in the patient's general condition
- is medically significant, i.e., defined as an event that jeopardizes the patient or may require medical or surgical intervention to prevent one of the outcomes listed above.

All malignant neoplasms will be assessed as serious under "medically significant" if other seriousness criteria are not met.

Unlike routine safety assessments, SAEs are monitored continuously and have special reporting requirements; see Section 7.2.

All adverse events should be treated appropriately. Treatment may include one or more of the following: no action taken (i.e., further observation only); study drug dosage adjusted/temporarily interrupted; study drug permanently discontinued due to this adverse event; concomitant medication given; non-drug therapy given. The action taken to treat the adverse event should be recorded on the Adverse Event CRF.

Once an adverse event is detected, it should be followed until its resolution or until it is judged to be permanent, and assessment should be made at each visit (or more frequently, if necessary) of any changes in severity, the suspected relationship to the study drug, the interventions required to treat it, and the outcome.

Information about common side effects already known about the investigational drug can be found in the Investigator Brochure (IB) or will be communicated between IB updates in the form of Investigator Notifications. This information will be included in the informed consent and should be discussed with the patient during the study as needed.

7.2 Serious adverse event reporting

Screen Failures

Note the following requirement for Screen Failures: SAEs occurring after the subject has provided informed consent until the time the subject is deemed a Screen Failure must be reported to Novartis.

Treated subjects

To ensure patient safety, every SAE, regardless of causality, occurring after the patient has provided informed consent and until 30 days after the patient has stopped study participation (defined as time of last dose of study drug taken or last visit whichever is the later) must be reported to Novartis within 24 hours of learning of its occurrence.

Any SAEs experienced after this 30 day period should only be reported to Novartis if the investigator suspects a causal relationship to the study drug.

To ensure patient safety, every SAE, regardless of causality, occurring after the patient has provided informed consent and until 30 days after the last study visit if there are post-treatment follow-up visits with no required procedures must be reported to Novartis within 24 hours of learning of its occurrence. Any SAEs experienced after the 30 day period should only be reported to Novartis if the investigator suspects a causal relationship to study treatment.

Recurrent episodes, complications, or progression of the initial SAE must be reported as follow-up to the original episode, regardless of when the event occurs. This report must be submitted within 24 hours of the investigator receiving the follow-up information. An SAE that is considered completely unrelated to a previously reported one should be reported separately as a new event.

Information about all SAEs (either initial or follow-up information) is collected and recorded on the Serious Adverse Event Report Form. The investigator must assess the relationship of any SAE to each specific component of the study treatment (if the study treatment consists of several components), complete the SAE Report Form in English, and send the completed, signed form by fax within 24 hours of the awareness of the SAE to the local CMO & PS Department and also a copy to the Novartis Medical Expert and/or Clinical Trial Leader (according to page 2). The telephone and fax numbers of the contact persons in the local Drug Safety and Epidemiology department, specific to the site, are listed on page 2 of this protocol and/or in the investigator folder provided to each site. The original copy of the SAE Report Form and the fax confirmation sheet must be kept with the case report form documentation at the study site. Follow-up information should be provided using a new paper SAE Report Form stating that this is a follow-up to a previously reported SAE.

Follow-up information provided should describe whether the event has resolved or continues, if and how it was treated, whether the treatment code was broken or not and whether the patient continued or withdrew from study participation. Each re-occurrence, complication, or progression of the original event should be reported as a follow-up to that event regardless of when it occurs.

If the SAE is not previously documented in the Investigator's Brochure or Package Insert (new occurrence) and is thought to be related to the investigational treatment a Drug Safety and Epidemiology Department associate may urgently require further information from the investigator for Health Authority reporting. Novartis may need to issue an Investigator Notification (IN) to inform all investigators involved in any study with the same investigational treatment that this SAE has been reported. Suspected Unexpected Serious Adverse Reactions (SUSARs) will be collected and reported to the competent authorities, relevant ethics committees and additional regulatory bodies as required for Gene Therapy studies (e.g the NIH in the United States) in accordance with Directive 2001/20/EC or as per national regulatory requirements in participating countries.

7.3 Liver safety monitoring

To ensure patient safety and enhance reliability in determining the hepatotoxic potential of an investigational drug, a standardized process for identification, monitoring and evaluation of liver events has to be followed.

Liver events are divided into two categories:

- Liver events of special interest (AESI) which consist of LFTs elevations
- Medically significant liver events which are considered as serious adverse events (SAEs) and which consist of marked elevations of LFTs and / or pre-specified adverse events.

Please refer to Table 15-1-Appendix 3 for complete definitions of liver events.

Any liver event which meets the criteria for a "**medically significant**" event should follow the **standard procedures for SAE reporting** as described in Section 7.2.

Every liver event as defined in Table 15-1-Appendix 3 should be followed up by the investigator or designated personal at the trial site, as summarized below and detailed in Table 15-2-Appendix 3.

- Repeating the LFT to confirm elevation as appropriate
- Discontinuation of the investigational drug if appropriate
- Hospitalization of the patient if appropriate
- A causality assessment of the liver event via exclusion of alternative causes (e.g., disease, co-medications)
- An investigation of the liver event which needs to be followed until resolution

Novartis	Confidential	Page 69
Amended Protocol Version v06 (Clean)		Protocol No. CCGF166X2201

These investigations can include serology tests, imaging and pathology assessments, hepatologist's consultancy, based on investigator's discretion. All follow-up information, and the procedures performed should be recorded as appropriate in the CRF.

7.4 Pregnancy reporting

To ensure patient safety, each pregnancy occurring while the patient is on study treatment must be reported to Novartis within 24 hours of learning of its occurrence. The pregnancy should be followed up to determine outcome, including spontaneous or voluntary termination, details of the birth, and the presence or absence of any birth defects, congenital abnormalities, or maternal and/or newborn complications.

Pregnancy should be recorded on a Clinical Trial Pregnancy Form and reported by the investigator to the local CMO & PS Department. Pregnancy follow-up should be recorded on the same form and should include an assessment of the possible relationship to the investigational/study treatment any pregnancy outcome. Any SAE experienced during pregnancy must be reported on the SAE Report Form.

Pregnancy outcomes must be collected for the female partners of any males who took study treatment in this study. Consent to report information regarding these pregnancy outcomes should be obtained from the mother.

7.5 **Prospective suicidality assessment**

The Columbia-Suicide Severity Rating Scale (C-SSRS), a questionnaire that prospectively assesses Suicidal Ideation and Suicidal Behavior using a semi-structured interview to probe patient responses, has to be administered.

If at any assessment after screening and/or baseline the score is 4 or above on the Suicidal Ideation item or any "yes" on the Suicidal Behavior item, the patient **must** be referred to a health care professional for further assessment and/or treatment. The decision on whether the study treatment should be discontinued is to be taken by the health care professional to whom the patient is referred.

7.6 Early phase safety monitoring

The Investigator will monitor adverse events in an ongoing manner and inform the Sponsor of any clinically relevant observations. Any required s will be made jointly between medically qualified personnel representing the Sponsor and Investigator. Such evaluations may occur verbally, but the outcome and key discussion points will be summarized in writing (e-mail) and made available to both Sponsor and all Investigator(s). Criteria pertaining to stopping the study/treatment or adapting the study design are presented above.

When two or more clinical site(s) are participating in the clinical study, the Sponsor will advise the Investigator(s) at all sites in writing (e-mail) (and by telephone if possible) of any new, clinically relevant safety information reported from another site during the conduct of the study in a timely manner.

8 Data review and database management

8.1 Site monitoring

Before study initiation, at a site initiation visit or at an investigator's meeting, a Novartis representative will review the protocol and CRFs with the investigators and their staff. During the study, the field monitor will visit the site regularly to check the completeness of patient records, the accuracy of entries on the CRFs, the adherence to the protocol and to Good Clinical Practice, the progress of enrollment, and to ensure that study drug is being stored, dispensed, and accounted for according to specifications. Key study personnel must be available to assist the field monitor during these visits.

The investigator must maintain source documents for each patient in the study, consisting of case and visit notes (hospital or clinic medical records) containing demographic and medical information, laboratory data, electrocardiograms, and the results of any other tests or assessments. All information on CRFs must be traceable to these source documents in the patient's file. The investigator must also keep the original informed consent form signed by the patient (a signed copy is given to the patient).

The investigator must give the monitor access to all relevant source documents to confirm their consistency with the CRF entries. Novartis monitoring standards require full verification for the presence of informed consent, adherence to the inclusion/exclusion criteria, documentation of SAEs, and the recording of data that will be used for all primary and safety variables. Additional checks of the consistency of the source data with the CRFs are performed according to the study-specific monitoring plan. No information in source documents about the identity of the patients will be disclosed.

8.2 Data collection

Designated investigator staff will enter the data required by the protocol into the Electronic Case Report Forms using fully validated software that conforms to 21 CFR Part 11 requirements. Designated investigator site staff will not be given access to the EDC system until they have been trained. Automatic validation programs check for data discrepancies and, by generating appropriate error messages, allow the data to be confirmed or corrected before transfer of the data to Novartis or the CRO working on behalf of Novartis. The Investigator must certify that the data entered into the Electronic Case Report Forms are complete and accurate. After database lock, the investigator will receive a CD-ROM or paper copies of the patient data for archiving at the investigational site.

All data captured for this study will have an external originating source (either written or electronic). The CRF is not considered as source.

8.3 Database management and quality control

All data should be recorded, handled and stored in a way that allows its accurate reporting, interpretation and verification.

Novartis staff or CRO working on Novartis's behalf will review the data entered into the eCRFs by investigational staff for completeness and accuracy and instruct the site personnel to make any required corrections or additions. Queries are sent to the investigational site using an electronic data query. Designated investigator site staff is required to respond to the query and confirm or correct the data. If the electronic query system is not used, a paper Data Query Form will be sent (e.g., fax, e-mail) to the site. Site personnel will complete and sign the copy, then send it (with original signature) back to Novartis staff who will make the correction to the database.

Concomitant medications entered into the database will be coded using the WHO Drug Reference List, which employs the Anatomical Therapeutic Chemical classification system. Medical history/current medical conditions and adverse events will be coded using the Medical dictionary for regulatory activities (MedDRA) terminology.

Laboratory samples will be processed centrally and the results will be sent electronically to Novartis (or a designated CRO).

Commercially Confidential Information

8.4 Data Safety Monitoring Board

A Data Safety Monitoring Board (DSMB) has been assembled for this compound to monitor safety data for the combined First In Man and Proof of Concept study. This committee is autonomous and comprises one external expert as well as selected Novartis associates who have subject matter expertise in auditory and vestibular clinical diagnosis, as well as general expertise in safety monitoring, monitoring of clinical trials, and statistical analysis and data visualization.

The DSMB will convene as outlined in the DSMB Charter to review adverse events, including clinical laboratory data, pure tone audiometry assessment and vestibular safety assessment will be continuously reviewed.

8.5 Adjudication Committee

Not required.

9 Data analysis

9.1 Analysis sets

For all analysis sets, patients will be analyzed according to the study treatment(s) received.

The safety analysis set will include all patients that received any study drug.

The PD analysis set will include all patients with available PD data and no protocol deviations with relevant impact on PD data.

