3.1 Study design

This non-confirmatory three part study utilizes an open label, single dose, sequential cohort design for the investigation of CGF166 and will be conducted in multiple centers.

The current study will evaluate the safety, tolerability, and potential efficacy of CGF166 and the associated delivery procedures in patients with severe-to-profound bilateral or unilateral hearing loss with intact vestibular function in the non-operative ear. Patients are required to have documented non-fluctuating severe-to-profound bilateral or unilateral hearing loss prior to enrollment. A maximum of 22 patients will be enrolled in this 3 Part, 5 cohort trial (Figure 3-1).

Novartis Amended Protocol Version v06 (Clean) Confidential

Page 40 Protocol No. CCGF166X2201

Part A

Part A will assess the safety and tolerability as well as potential efficacy following a single IL dose of 20 uL of CGF166 concentration Commercially Confidential Patient enrollment will be staggered so that a safety data review can be done after each treated patient (~4 weeks after treatment) prior to dosing each subsequent patient.

Part B

Part B will include a volumetric escalation design to evaluate up to 3 infusion volumes (between 20 and 60 μ L) of the same CGF166 concentration^{Commercially Confidential} 3 cohorts of patients (n=3/cohort; total of 9 patients). All dose volumes are subject to change based on trial safety data.

Each subsequent cohort will be dosed only after the volume delivered in the prior cohort is deemed to be safe and tolerable as determined by the Drug Safety Monitoring board (DSMB). The DSMB will consist of internal Novartis personnel as well as at least one external subject matter expert who is not serving as an investigator or otherwise privy to trial data. The membership and workings of the DSMB will be detailed in the DSMB Charter. In addition, the scheduling and dosing of the first patient in each cohort will be staggered to allow at least a four week interval in between treating the remaining 2 patients in each cohort.

Part C

Considering the preliminary overall review of the data including changes observed in audiometry for patients from Cohort 1 through Cohort 4, the DSMB endorsed the team's proposal that $30 \ \mu L$ is the maximum tolerated dose (volume) observed in the study.

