3.6.2 Risks of general anesthesia and stapedotomy surgery

Foreseeable risks for the administration of CGF166 are largely those known for general anesthesia, which are uncommon, and those associated with modern stapedotomy.

In published series that describe stapedotomy outcomes, many patients experience transient vestibular symptoms that are procedure-related including dizziness and nausea. Post-operatively, it is possible that symptoms and signs of vestibular dysfunction may be more frequent or more severe than are usually observed after stapedotomy, or may persist for a longer period of time. Strategies to avoid patient Valsalva maneuvers and possible effects on the stapedotomy plug or the re-positioned tympanic membrane are important. Such preemptive approaches might include treatment with dexamethasone and anti-histamines, for example.

Known surgical risks of mild to moderate severity include persistent alteration of taste due to injury of the chorda tympani, infectious otitis media, perilymph fistula, reparative granuloma and perforation of the tympanic membrane, and worsened hearing. Each of the foregoing items carries a risk of 5% or less. Rare, but more serious adverse effects include facial nerve palsy, infective labyrinthitis or meningitis.

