5.5.5 Permitted dose adjustments and interruptions of study treatment

Study drug dose adjustments and/or interruptions are not permitted, unless during surgical procedure the surgeon deems the patient ineligible or is unable to dose the patient.

In case of notable adverse events and safety concerns during dose escalation of the study, the following changes to the next planned dose level may be considered:

- Administration of a dose below the starting dose
- Administration of an intermediate dose between the current and preceding dose
- Administration of an intermediate dose between the current and next planned dose
- Repeated administration of the current dose
- Termination of any further dose escalation

These changes must be recorded on the Dosage Administration Record CRF.

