5.5.10 Discontinuation of study treatment and premature patient withdrawal

Study and cohort "Stopping rules"

The study will be put on hold and no new patients dosed pending a full safety review if any of the following criteria should be met:

- 3 or more patients with study drug-related or surgical procedure-related SAEs are reported
- At least 2 patients in the same cohort experience a similar AE which is assessed as severe in intensity, and is related to the study drug or surgical procedure
- Clinical evidence of post-operative vestibular dysfunction of moderate severity (impairs instrumental activities of daily living, such as preparing meals or housework) that persists longer than 4 weeks in 2 patients.
- •

- 1 patient develops a severe systemic immune response attributed to study drug
- 1 patient develops a severe infection consistent with those caused by adenovirus (if confirmed to be related to study drug).

Individual patient withdrawal

Patients may voluntarily withdraw from the study for any reason at any time. They may be considered withdrawn if they state an intention to withdraw, fail to return for visits, or become lost to follow-up for any other reason.

Confidential

If a patient withdrawal occurs for any reason, the investigator must make every effort to determine the primary reason for a patient's withdrawal from the study and record this information on the CRF.

The investigator should withdraw the patient from study if, on balance, he/she believes that continuation would be detrimental to the patient's well-being. A patient may withdraw consent from the study at any time.

A decision to not administer the single dose study treatment and patient withdrawal will be at the discretion of the Investigator, under the following circumstances:

- Complication during surgery or patient ear anatomy does not allow the surgeon to properly administer the dose infusion
- Use of prohibited treatment
- Any other protocol deviation that results in a significant risk to the patient's safety

Patients who discontinue study treatment should NOT automatically be considered withdrawn from the study. As single dose gene therapy, every effort will be to follow up with all treated patients whom have discontinued for whatever reason. See Section 6 for the required assessments of these patients after discontinuation of study treatment.

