9.4.2 Statistical model, hypothesis, and method of analysis

Tone thresholds will be analyzed for each frequency tested separately.

For pure tone audiometry, a measure that depends on a patient being able to hear a tone, the following imputation will be done: If a patient is unable to hear the tone at a specific frequency it can be inferred that the threshold value exceeds the upper limit of the machine. In this case the value will be imputed to 5dB above the upper limit of the machine.

All pure tone audiometry air conduction threshold data will be listed and graphically displayed by patient, infusion volume, frequency, and visit/time. Summary statistics will be provided by infusion volume, frequency, ear and visit/time. Change from baseline of the thresholds (mean of screening and baseline visit) will also be summarized by infusion volume, frequency, ear and visit/time.

In addition, safety and tolerability is a co-primary endpoint, and will be analyzed as in Section 9.5.2 (Safety).

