9.5.2 Safety

Vital signs

All vital signs data will be listed by treatment, patient, and visit/time and if ranges are available abnormalities (and relevant orthostatic changes) will be flagged. Summary statistics will be provided by treatment and visit/time.

ECG evaluations

All ECG data will be listed by treatment, patient and visit/time, abnormalities will be flagged. Summary statistics will be provided by treatment and visit/time.

Clinical laboratory evaluations

All laboratory data will be listed by treatment, patient, and visit/time and if normal ranges are available abnormalities will be flagged. Summary statistics will be provided by treatment and visit/time.

Adverse events

All information obtained on adverse events will be displayed by treatment and patient.

The number and percentage of patients with adverse events will be tabulated by body system and preferred term with a breakdown by treatment. A patient with multiple adverse events within a body system is only counted once towards the total of this body system. Exact 95% binomial confidence intervals may be provided for AE rates. If a dose-related safety signal is suspected, this may be confirmed by a permutation contrast test t using the nominal dose level as contrast.

Confidential

Other safety evaluations

Not applicable.

Commercially Confidential Information

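### The safety set counts only dosed patients, so a surgical complication that prevents dosing is recorded but has no place in the adverse event rates

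*Protocol*

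**What the plan says.** **Analysis set.** Protocol 9.1: "The safety analysis set will include all patients that received any study drug". The same section groups patients in every set by the treatment they received. SAP section 5 also requires receipt of study drug, and it leaves out patients whose protocol deviations bear on safety. The text that follows there is blacked out.

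**Rates and listings.** Protocol 9.5.2: "The number and percentage of patients with adverse events will be tabulated by body system and preferred term with a breakdown by treatment". SAP 8.1 breaks the same table down by infusion volume where that applies. Neither section names the analysis set, but no other safety set is visible. Both also plan a patient-level display of all AE information.

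**What is being evaluated.** Protocol 3.1 says the study will "evaluate the safety, tolerability, and potential efficacy of CGF166 and the associated delivery procedures" and makes the start of Part C depend on the safety of the delivery methods as well as of the drug. Protocol 3.6.2: "Foreseeable risks for the administration of CGF166 are largely those known for general anesthesia, which are uncommon, and those associated with modern stapedotomy". Protocol 9.4.2 adds that "safety and tolerability is a co-primary endpoint".

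**Surgery without dosing.** Protocol 5.5.10 lists among the grounds for not giving the dose: "Complication during surgery or patient ear anatomy does not allow the surgeon to properly administer the dose infusion". Protocol 5.5.5 bars dose adjustments "unless during surgical procedure the surgeon deems the patient ineligible or is unable to dose the patient".

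**Event capture.** AEs are recorded from consent (protocol 7.1) and SAEs are reportable from consent whatever the cause (7.2). One hold criterion in 5.5.10 is that "3 or more patients with study drug-related or surgical procedure-related SAEs are reported"; it does not require that a dose was given.

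**The concern.** A patient who is anesthetized and operated on has met the risks that the protocol itself calls the main foreseeable ones, whether or not CGF166 follows. If a complication stops the infusion, that complication is also what keeps the patient out of the safety set. Membership of the set then depends on the outcome being counted: the patient leaves both numerator and denominator. An event could count toward a study hold and still be missing from the AE percentages that describe a co-primary endpoint. What is at stake is the reported rate of surgical and anesthetic complications. The rate of events caused by the drug is not at stake, because an undosed patient cannot contribute to it.

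**Working it through.** **1. Sizes.** Protocol 3.1 gives 3 patients in Part A, 3 × 3 = 9 in Part B and 10 in Part C. The sum, 3 + 9 + 10 = 22, reproduces the stated maximum. SAP 2.2 still gives larger Parts B and C (12, and 20 to 30); the amended protocol's sizes are used here. Protocol 5.2 says Parts A and B are complete, so the exposure going forward is mainly the 10 Part C surgeries.

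**2. Following one operated, undosed patient through the plan.**
- Collected: yes (7.1, 7.2).
- Can count toward the hold rule: yes, if the event is a procedure-related SAE (5.5.10).
- May appear in the AE listing: yes (9.5.2, SAP 8.1).
- In the 9.1 safety set: no.
- Has a treatment or infusion-volume column in the AE table: no.

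**3. Effect on the rate when complications are the only reason for not dosing.** Let n patients be operated on, x have a complication, and k of those x go undosed because of it. The rate among operated patients is x/n; the reported rate is (x − k)/(n − k). Cross-multiplying, (x − k)/(n − k) ≤ x/n whenever x ≤ n, with equality only if k = 0 or x = n.

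Exact (Clopper-Pearson) 95% intervals, the type that 9.5.2 allows:

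| Illustration in Part C | Among operated | As reported, among dosed |
|---|---|---|
| 1 complication, which prevents dosing | 1/10 = 10.0% (0.3 to 44.5%) | 0/9 = 0% (0 to 33.6%) |
| Same, patient replaced so that 10 are dosed | 1/11 = 9.1% (0.2 to 41.3%) | 0/10 = 0% (0 to 30.8%) |
| 2 complications, 1 of which prevents dosing | 2/10 = 20.0% (2.5 to 55.6%) | 1/9 = 11.1% (0.3 to 48.2%) |

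The second row is needed because 5.5.10 rules out replacement only for withdrawals unrelated to safety or lack of efficacy.

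In the long run, with complication risk p and a share f of complications that prevent dosing, the reported rate is p(1 − f)/(1 − pf). For f = 25%, 50% and 75%, p = 5% is reported as 3.8%, 2.6% and 1.3%, and p = 10% as 7.7%, 5.3% and 2.7%. Both p and f are assumptions. The figure of 5% or less per item in 3.6.2 is not the rate of complications that prevent dosing.

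**4. Effect when others go undosed too.** Let m further patients without a complication be undosed, for anatomy or ineligibility. The reported rate becomes (x − k)/(n − k − m), which exceeds x/n when xm > k(n − x). Example: n = 10, x = 3, k = 1, m = 3. Then 3 × 3 = 9 exceeds 1 × 7 = 7, and 3/10 = 30% is reported as 2/6 = 33%.

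**5. How likely.** The documents give no rate. If the risk of a dose-preventing complication is assumed to be 1%, 2%, 5% or 10% per surgery, the chance of at least one in 10 surgeries, 1 − (1 − p)^10 with p now that risk, is 9.6%, 18.3%, 40.1% or 65.1%.

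**The case against.** The strongest reply is that little is lost. The event is recorded, reported if serious, counted by the hold rule where relevant, and can be shown in the patient-level listing. With 10 patients, that listing is a main safety display. The trial is non-confirmatory, AE reporting is descriptive, and no visible decision rule uses the AE percentage. A hold count and an AE table serve different purposes and need not agree. All of this stands and limits the weight of the point, but it preserves the event and not the rate.

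Three narrower replies:
- *The glossary defines study drug as any drug given in the required study procedures, which might take in anesthetics.* Protocol 5.1.2 requests no treatment beyond the investigational one, so this reading does not bring the patient into the set.
- *The SAP breaks AEs down by volume only where that applies.* This leaves room for an undosed patient but does not say that one will be counted, or in which denominator.
- *The blacked-out text in SAP section 5 may define a set of operated patients.* It may. The SAP part of the fix is conditional for that reason.

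Two stronger inferences are tempting. A reader might conclude that the reported surgical complication rate is always too low when a complication prevents dosing. The documents do not support this, because anatomy and ineligibility are also foreseen reasons for not dosing, and step 4 of the working shows that the rate can then rise. A reader might also infer that surgical complications in general drop out. They do not: the set takes any patient who received any study drug, so complications in fully or partly dosed patients stay in the rates.

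**Conclusion.** The point holds as a gap in the rates. As the visible text stands, an operated but undosed patient belongs to no safety set and to no column of the AE table, although the delivery procedure is under evaluation and safety is co-primary. If complications are the only reason for not dosing, one such patient in Part C turns 1/10 into 0/9, or 1/11 into 0/10 with replacement. The direction is not fixed once other reasons for not dosing occur.

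This rests on three things: that the AE table uses the 9.1 safety set, which is an inference from the absence of any other; that the blacked-out SAP text does not already define a suitable set; and that at least one surgery ends without dosing. The documents give no frequency and do not say whether any surgery in Parts A or B was aborted. If every operated patient is dosed, no rate changes. The intervals at these sizes are wide and overlap heavily, so the reason to act is the outcome-dependent exclusion, which costs little to remove, and not a demonstrated large bias.

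**What to change.** Keep the dosed safety set for the summaries by infusion volume. Then:

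- **Protocol 9.1:** add a surgical safety set, defined as all patients in whom study anesthesia or surgery was started, whether or not CGF166 was given.
- **SAP section 5:** add the same set, unless the blacked-out text already defines it.
- **Protocol 9.5.2 and SAP 8.1:** name the set behind each AE table. Tabulate AEs and SAEs for the surgical safety set, overall and with a separate column for patients operated on but not dosed. Report the numbers operated on and dosed, with the reason for each patient not dosed.

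The cost is one added set and one added table column. No patients, visits or data are added, because AEs are already collected from consent, and the planned columns by infusion volume do not change. SAP 1.2 allows such a change through version control before database lock. If no surgery was aborted, the report can say in one line that the numbers operated on and dosed are equal.
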